3.3.4 Medical History

Medical history will be coded to system organ class and preferred term using the Medical Dictionary for Regulatory Activities (MedDRA) version 21.0. Counts and percentages of subjects with medical history by system organ class and preferred term will be summarized by treatment assignments in the double-blind phase and in total based on Safety Analysis Set.

3.3.5 Concomitant Medications

Concomitant medications will be coded to anatomical therapeutic chemical (ATC) class and preferred term using the World Health Organization Drug (WHODrug) Dictionary Mar 2018 Global B3 version. For summary purposes, medications will be considered prior medications if they stopped prior to the first dose of study drug (lead-in infusion) and concomitant medications if they were taken at any time after the first dose of study drug (lead-in infusion) (i.e. started prior to the first dose of study drug and were ongoing or started after the first dose of study drug).

Counts and percentages of subjects taking prior and concomitant medications by ATC class and preferred term will be summarized by treatment assignments in the double-blind phase and in total based on the Safety Analysis Set.

3.3.6 Study Duration and Drug Exposure

Study duration will be calculated as the date of last visit – date of first dose (lead-in phase) + 1. Study duration will be summarized with descriptive statistics by treatment assignments in the double-blind phase and in total. Additionally, study duration will be categorized according to the following categories:

- 1 to 15 days,
- 16 to 29 days, and
- >29 days.

A summary of subjects receiving the study drug will be provided by treatment assignments in the double-blind phase and in total for each visit on the Safety Analysis Set and Full Analysis Set.

The number of infusions for each subject will be summarized with counts and percentages by treatment assignments in the double-blind phase and in total on the Safety Analysis Set and Full Analysis Set.

3.4 Efficacy Assessment

All efficacy analyses will be based on the Full Analysis Set and all statistical tests will be 2-sided hypothesis tests performed at the 5% level of significance. Also, all confidence intervals will be 2-sided 95% confidence intervals, unless stated otherwise. All the efficacy analyses will be performed on the assigned treatments in the double-blind phase.

3.4.1 Primary Efficacy Endpoints

Primary Analysis

The primary efficacy variable is defined as the change from baseline PCWP with bicycle exercise (25 watts) at 6 weeks. The baseline PCWP with bicycle exercise (25 watts) is defined as the value obtained prior to lead-in study drug infusion at Visit 1.

The primary efficacy analysis will be conducted over the Full Analysis Set. The PCWP will be analyzed using an analysis of variance (ANOVA) model with change from baseline to Week 6 in PCWP as dependent variable, treatment group as a factor.

An example of SAS code is provided below:

```
*****

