2.2 Study Design

2.2.1 *Overview*

[figure not shown]
This study will be conducted at approximately 20-25 sites in the United States. The Phase 2 study of levosimendan in PH-HFpEF subjects has been designed in two phases (Figure 1). The study will recruit male and female subjects meeting identified enrollment criteria for PH-HFpEF into the lead-in open label phase to identify “responders” to levosimendan intravenous infusion of at 0.10 µg/kg/min for 24 hours \pm 30 min. Subjects that have clinically relevant responses to levosimendan will be randomized to levosimendan or placebo (1:1) and receive intermittent (weekly) study drug infusions (Week 2-5). The first 36 subjects who demonstrate a \geq 4mmHg reduction in PCWP from baseline measured at bicycle exercise (25 watts) with no more than a 10% decrease from baseline in cardiac index will be classified as a “responder” to the

lead-in levosimendan dose and be randomized to the double-blind phase of the study. Patients who do not tolerate the initial levosimendan infusion due to excessive hypotension or tachycardia will be dropped from eligibility. In the double-blinded phase, patients will be randomized to levosimendan or placebo and receive a weekly dose of study drug intravenously at $0.075 \mu\text{g}/\text{kg}/\text{min}$ for 24 hours ± 30 min and if tolerated titrated to $0.10 \mu\text{g}/\text{kg}/\text{min}$ for 24 hours ± 30 min at Week 4. The infusion rate of study drug may be decreased or interrupted as clinically warranted if the subject has hypotension, tachycardia, or signs or symptoms consistent with hypovolemia (e.g., low systolic blood pressure [SBP], decreasing urine output with rising blood urea nitrogen [BUN] and serum creatinine) Record the time of discontinuation or down titration. Patients should be monitored closely until clinically stable. See Protocol Attachment 1 for infusion rates and instructions on dose adjustments. Patients will be evaluated Week 6 to determine the efficacy and safety of levosimendan. Randomized subjects that have not received study drug weekly through Week 5 and returned for evaluation on Week 6 will be replaced to ensure 18 subjects have completed in each study group.

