2.3.2 Secondary Efficacy Endpoints

- Change in Cardiac Index at rest and with exercise at Week 6
- Change in PVR effect at rest and with exercise at Week 6
- Change in PCWP when supine and legs elevated at Week 6
- Change in mean pulmonary artery pressure (mPAP) effect at rest and with exercise at Week 6
- Change in right atrial pressure (RAP) effect at rest and with exercise at Week 6
- Patient global assessment (based on a six-point Likert scale) at Week 6
- 6MWT at Week 6 (distance)
- Physician's Assessment of Functional Class
- Clinical Events: Death and hospitalizations

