3 STATISTICAL METHODOLOGY

3.1 General Considerations

3.1.1 *Study Day*

Study day will be calculated from the date of first dose of study drug (lead-in infusion). The day of the first dose of study drug will be Day 1, and the day immediately before Day 1 will be Day -1. There will be no Day 0.

3.1.2 *Definition of Baseline*

Baseline is defined as the value obtained prior to lead-in study drug infusion on Visit 1. Note: The protocol-specified visit ‘Day 0’ will be referred to as ‘Visit 1’ for analysis purposes.

3.1.3 *Analysis Visit Windows*

Post-baseline assessments will be assigned a visit number based on the study day. Analysis visit windows will be defined as below:

- Screening: ≤ 28 Days Prior to Visit 1,
- Lead-In Visit: Visit 1/Week 1/Day 1,
- Visit 2/Week 2/Day 8: Day 2 to Day 11,
- Visit 3/Week 3/Day 15: Day 12 to Day 18,
- Interim Office Visit: Between Visit 3/Week 3 and Visit 4/Week 4,
- Visit 4/Week 4/Day 22: Day 19 to Day 25,
- Visit 5/Week 5/Day 29: Day 26 to Day 32, and
- Visit 6/Week 6/Day 36: Day 33 or later.

3.1.4 *Summary Statistics*

Categorical data will generally be summarized with counts and percentages of subjects. The denominator used for the percentage calculation will be clearly defined. Continuous data will generally be summarized with descriptive statistics including n (number of non-missing values), mean, median, standard deviation, minimum, and maximum.

3.1.5 *Handling of Dropouts and Missing Data*

In cases of missing or incomplete data (e.g. adverse event [AE] and concomitant medications), the missing component(s) will be assumed as the most conservative value possible. For example, AEs with missing start dates, but with stop dates either overlapping into the treatment period or missing, will be counted as treatment-emergent, taking the worst-case approach. When partial dates are present in the data, both a partial start date and/or a partial stop date will be evaluated to determine whether it can be conclusively established that the AE started prior to the start of study drug or ended prior to the start of study drug. If the above cannot be conclusively established based on the partial and/or present dates, then the AE will be considered as treatment-emergent. Actual data values as they appear in the original eCRF will be presented in the data listings. Missing values for other variables will not be imputed and only observed values will be used in data analyses and presentation.

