** PCWP = Change in PCWP from Baseline **
** TREATMENT = Treatment group where 0 if Placebo, 1 if Levosimendan **
*****
PROC GLM;
  CLASS TREATMENT;
  MODEL PCWP = TREATMENT;
  LSMEANS TREATMENT / E PDIFF CL STDERR ALPHA=0.05;
  ESTIMATE 'LEVOSIMENDAN VS PLACEBO' TREATMENT 1 -1 / E;
RUN;
```

Sensitivity Analyses

Sensitivity Analyses 1: A sensitivity analysis will include an adjustment for baseline. The PCWP will be analyzed using an analysis of covariance (ANCOVA) model with change from baseline to Week 6 in PCWP as dependent variable, treatment group as a factor and baseline as a covariate.

Sensitivity Analyses 2: A sensitivity analysis by acetylation status. The PCWP with bicycle exercise (25 watts) at 6 weeks will be analyzed using an ANOVA with change from baseline to Week 6 in PCWP as dependent variable, treatment group and the acetylation status (fast, intermediate, and slow) as factors.

Supportive Analyses

An additional primary endpoint analysis will be repeated on the Per-Protocol Set.

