3.4.2 Secondary Efficacy Endpoints

The secondary efficacy analyses will be performed on the Full Analysis Set.

Analyses of hemodynamic endpoints will be performed using the same ANOVA model as the primary endpoint. Series Plots will be provided for PCWP by position and visit.

Patient global assessment (based on a six-point Likert scale) at Week 6 will be performed by a Mann-Whitney-Wilcoxon test for each of the six symptom's grade. Total score will be calculated as the sum of all 6 scores for the subjects with all 6 scores available.

6MWT exercise distance at Week 6 will be tested using the same ANOVA model as the primary endpoint.

Physician's assessment of New York Heart Association (NYHA) functional class (Class I to IV) will be summarized at each time point by treatment group as a shift table from baseline to post-baseline time point. Percentages will be based on the number of subjects with both a baseline and post-baseline (at the specific time point) assessment. The treatment difference of physician's assessment of functional class at Week 6 will be tested using the two-sided Pearson's chi-squared test.

The incidence of death and hospitalization will be summarized by treatment group. Two-sided 95% CIs for the observed difference in clinical events: death and hospitalizations between the treatment groups will be presented based on a continuity-correct Z-statistic. A by-subjects listing of subjects who died due to any cause will be provided.

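### Primary, haemodynamic and 6MWT analyses leave out the collected baseline as a covariate: a cheap precision gain of uncertain size, not an error

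*SAP*

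**What the plan says.** SAP Section 3.4.1 specifies for the primary endpoint an "analysis of variance (ANOVA) model with change from baseline to Week 6 in PCWP as dependent variable, treatment group as a factor". The sample SAS code agrees: "MODEL PCWP = TREATMENT". Under Sensitivity Analyses in the same section, "A sensitivity analysis will include an adjustment for baseline"; this is an ANCOVA of the same change score, for exercise PCWP only.

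Section 3.4.2 extends the treatment-only model: "Analyses of hemodynamic endpoints will be performed using the same ANOVA model as the primary endpoint", and "6MWT exercise distance at Week 6 will be tested using the same ANOVA model as the primary endpoint". No adjusted analysis is planned for these endpoints.

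The baselines exist. Section 3.1.2 states: "Baseline is defined as the value obtained prior to lead-in study drug infusion on Visit 1". Section 3.3.3 lists baseline PCWP, Cardiac Index, PVR, mean PAP, RAP and 6MWT distance among the variables to be summarised. All precede randomization, because the lead-in infusion does.

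Section 2.2.1 makes the same baseline part of the entry rule for the double-blind phase: responders need at least a 4 mmHg "reduction in PCWP from baseline measured at bicycle exercise (25 watts) with no more than a 10% decrease from baseline in cardiac index".

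**The concern.** A change score uses the baseline with its coefficient fixed in advance. ANCOVA estimates that coefficient. Where the fixed value is not the best one, part of the variation that baseline could explain stays in the residual, and the confidence interval is wider than the collected data allow. With 18 subjects per arm that can matter.

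The trial will produce the adjusted estimate for exercise PCWP, but the unadjusted one decides. For the secondaries no adjusted estimate is planned.

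**Working it through.** **Inputs from the SAP.** 36 randomized 1:1, SD 5 mmHg, difference 4.9 mmHg, two-sided 0.05, 80% power (Section 2.2.3). Dropouts are replaced so that 18 per arm complete (Section 2.2.1).

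**Assumed, because the SAP does not give them.** The correlation rho between baseline and Week 6, from 0.3 to 0.9; the ratio k of Week 6 SD to baseline SD, at 0.8, 1 and 1.2; and that 5 mmHg is the SD of change. Section 2.2.3 does not say whether it is the SD of the value or of the change.

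**Step 1: the plan's own figure.** SE = 5 × √(2/18) = 1.667 mmHg. Noncentrality = 4.9/1.667 = 2.94. With 34 df, power is 81.5%; 17 per arm gives 79.1%. The stated 80% reproduces. The mean 95% CI half-width is 3.36 mmHg.

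**Step 2: what ANCOVA changes.** Without selection, the ratio of ANCOVA to ANOVA residual variance is k²(1 − rho²)/(1 + k² − 2·rho·k). For k = 1 this is (1 + rho)/2. Against it stand one df (34 to 33) and a chance-imbalance factor of 1 + 1/(36 − 4) = 1.031. Example at rho 0.5, k = 1: 0.75 × 1.031 = 0.773; SE = 5 × √0.773 × √(2/18) = 1.466; noncentrality = 4.9/1.466 = 3.34; power 90.1%.

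The formula also shows when nothing is gained: the ratio is 1 when rho × k = 1. At k = 1.2 and rho 0.8 it is 0.518/0.520 = 0.997. At k = 0.8 and rho 0.9 it is 0.122/0.200 = 0.61.

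**Step 3: responder selection.** Subjects enter on a fall from this same baseline, which with equal SDs reduces the gain. Baseline, lead-in and Week 6 values were simulated as trivariate normal with common rho, kept if the lead-in fall was at least 4 mmHg, and rescaled so that the SD of change is 5. Ranges below cover a single-value SD of 5 or 7 mmHg and a mean lead-in fall of 2 or 6 mmHg; k is the ratio before selection.

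ANCOVA power (%), against 81.5% for the ANOVA:

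| rho | No selection, k = 1 | Selection, k = 1 | Selection, k = 1.2 | Selection, k = 0.8 |
|---|---|---|---|---|
| 0.3 | 93.6 | 89.5–90.7 | 85.6–86.5 | 94.5–95.5 |
| 0.5 | 90.1 | 86.1–87.2 | 82.8–83.2 | 92.8–94.0 |
| 0.7 | 86.3 | 83.7–84.1 | 80.2–81.0 | 91.6–92.8 |
| 0.8 | 84.2 | 82.3–83.4 | 80.1–80.6 | 92.3–92.9 |
| 0.9 | 82.0 | 81.1–82.0 | 81.9–82.7 | 94.4–94.9 |

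With selection and k = 1, the CI half-width is 2.93–2.99 mmHg at rho 0.3, 3.10–3.14 at 0.5, 3.23–3.27 at 0.7, 3.29–3.32 at 0.8 and 3.35–3.37 at 0.9, against 3.36.

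**Step 4: the downside.** If baseline does not predict change at all, ANCOVA power is 80.2%, a loss of 81.5 − 80.2 = 1.3 points. Simulated type I error, without selection, was close to 5% for both models.

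**Step 5: the other reading of the SD.** If 5 mmHg is the SD of PCWP itself, the SD of change is 5√(2(1 − rho)) and the ANCOVA residual SD is 5√(1 − rho²). Without selection and with k = 1, ANOVA against ANCOVA power is 67.5% against 83.8% at rho 0.3, 81.5% against 90.1% at 0.5, and 95.8% against 97.6% at 0.7.

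**The case against.** **This is a preference.** The ANOVA is unbiased under randomization, text and code agree, the sample size is right for it, and the adjusted primary estimate will be reported anyway. All of that stands, and it is why this is not an error. It does not remove the point: the ANOVA result decides, the secondaries have no adjusted analysis, and the change costs very little.

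**The size of the gain is unknown.** This stands in full. It depends on the SD ratio as much as on the correlation, and nothing in the SAP selects a row or column of the table. A single headline gain would be unsupported.

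**Two stronger readings are tempting.**
- A reader might infer from Section 5 that a change to the primary model was hidden: it reports a protocol model with treatment and site and describes the change as one of name. But Section 5 summarises superseded protocol text, a model with only those two factors is an ANOVA, and the current text and code of Section 3.4.1 agree on treatment alone. No planned analysis contains site, so the power of a site model is not a consequence for this trial. What remains is one missing line of disclosure.
- A reader might infer that the 6MWT outcome is undefined, since Section 2.3.2 lists "6MWT at Week 6 (distance)" without the word change. Section 3.4.2 applies the primary model, whose dependent variable is a change, so change is the natural reading. Section 5 explains the wording as a clarification of duration to distance. This is at most a clarification.

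**Conclusion.** The point holds as a conditional, low-cost improvement. The planned ANOVA is valid and its stated power is correct; nothing here shows bias or an underpowered design.

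With 5 mmHg as the SD of change, responder selection and equal SDs, adjustment gains about 9 points of power at rho 0.3, 5 at 0.5, 2 at 0.7 and almost nothing from 0.8. That gradient belongs to equal SDs only. If Week 6 values are more variable than baseline (k = 1.2), the result runs from about 5 points gained to about 1 lost. If they are less variable (k = 0.8), the gain is 10 points or more at every correlation examined. The possible loss is about 1 point throughout, so the balance favours adjustment even though its size cannot be fixed from the SAP.

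**What to change.** Before database lock and while blinded:

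- Make change in exercise PCWP on treatment plus baseline exercise PCWP the primary analysis, and keep the present ANOVA as the sensitivity analysis.
- Use the same ANCOVA, each with its own baseline, for the haemodynamic secondaries and 6MWT distance. The treatment contrast is then the same whether the 6MWT outcome is change or the Week 6 value; name one for clarity.
- Record the new covariate in Section 5 and, as housekeeping, add that the protocol's site effect is not in the model. No site effect should be restored.

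The cost is one residual degree of freedom, the small chance-imbalance penalty, minor programming and a documented change of primary model. Analysing change already requires the baseline value, so no subject is lost from those analyses by adding it as a covariate. If the sponsor keeps the ANOVA as primary, the Section 5 line on site and the 6MWT wording are still worth adding.

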** PCWP = Change in PCWP from Baseline **
** TREATMENT = Treatment group where 0 if Placebo, 1 if Levosimendan **
*****
PROC GLM;
  CLASS TREATMENT;
  MODEL PCWP = TREATMENT;
  LSMEANS TREATMENT / E PDIFF CL STDERR ALPHA=0.05;
  ESTIMATE 'LEVOSIMENDAN VS PLACEBO' TREATMENT 1 -1 / E;
RUN;
```

Sensitivity Analyses

Sensitivity Analyses 1: A sensitivity analysis will include an adjustment for baseline. The PCWP will be analyzed using an analysis of covariance (ANCOVA) model with change from baseline to Week 6 in PCWP as dependent variable, treatment group as a factor and baseline as a covariate.

Sensitivity Analyses 2: A sensitivity analysis by acetylation status. The PCWP with bicycle exercise (25 watts) at 6 weeks will be analyzed using an ANOVA with change from baseline to Week 6 in PCWP as dependent variable, treatment group and the acetylation status (fast, intermediate, and slow) as factors.

Supportive Analyses

An additional primary endpoint analysis will be repeated on the Per-Protocol Set.

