2.2.3 Sample Size Calculation and Power Considerations

The sample size was estimated for the primary comparison of levosimendan and placebo using SAS (v9.4) for windows procedure PROC POWER.

A total of 36 randomized subjects (at 1:1 levosimendan vs. placebo) will provide 80% power to detect the difference at two-sided 0.05 level, assuming a standard deviation (SD) of 5 mmHg in PCWP and a treatment difference of ≥ 4.9 mmHg.

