6 PROGRAMMING SPECIFICATIONS

Analyses will be performed using SAS® version 9.3 or higher. All available data will be presented in subject data listings which will be sorted by subject and visit date as applicable. Detailed Programming Specifications will be provided in a separate document.

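### The example SAS code for the primary analysis labels a contrast levosimendan versus placebo but computes placebo minus levosimendan

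*SAP*

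**What the plan says.** Section 3.4.1 of the SAP analyses the change in exercise PCWP at Week 6 by a one-way ANOVA on treatment group. It then offers code, introduced with the words "An example of SAS code is provided below". The elements that matter are these:

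- The header comment fixes the coding: "TREATMENT = Treatment group where 0 if Placebo, 1 if Levosimendan".
- The `CLASS` statement names the treatment variable only. There is no `ORDER=` option and no format in the step.
- The arm means and their difference come from "LSMEANS TREATMENT / E PDIFF CL STDERR ALPHA=0.05".
- The labelled comparison is "ESTIMATE 'LEVOSIMENDAN VS PLACEBO' TREATMENT 1 -1 / E".

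Section 3.4 adds that "all confidence intervals will be 2-sided 95% confidence intervals, unless stated otherwise". Section 3.4.2 carries the model to the secondary endpoints: "Analyses of hemodynamic endpoints will be performed using the same ANOVA model as the primary endpoint". The 6-minute walk distance is handled the same way. Section 6 says of the programming that "Detailed Programming Specifications will be provided in a separate document". No section says which arm is subtracted from which.

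**The concern.** `ESTIMATE` applies its coefficients to the class levels in sorted order. With 0 and 1 as the levels, +1 falls on placebo and -1 on levosimendan. The label names the arms the other way round, and by ordinary convention a reader takes the first-named arm minus the second.

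The dependent variable is a change score, and section 2.2.1 treats a fall in PCWP as response. A true benefit is therefore a negative levosimendan-minus-placebo difference. The code as written would print it as a positive number and, read by its label, it would look like a rise in PCWP on levosimendan. A true harm would look like a benefit. The tests are two-sided, so the p-value does not show the direction; the sign of the estimate has to.

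If the line travels with the model to the secondary endpoints, the sign is reversed there too. The favourable direction is not the same for all of them: lower is better for PCWP, longer is better for walking distance. No single mental correction would serve.

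**Working it through.** **Inputs**

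- Coding 0 = placebo, 1 = levosimendan; plain `CLASS`; coefficients 1 and -1 (code in section 3.4.1).
- Difference 4.9 mmHg, SD 5 mmHg, 36 subjects at 1:1, so 18 per arm; two-sided 0.05; 80% power (section 2.2.3, "assuming a standard deviation (SD) of 5 mmHg in PCWP and a treatment difference of" 4.9 mmHg or more).
- Assumption: the variable is unformatted, as the code shows it.
- For illustration, arm means of 0 for placebo and -4.9 for levosimendan. Only their difference matters.

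**Step 1. Reproduce the SAP's own figure.** The two-sample t-test with the noncentral t distribution gives power of 81.5% at 18 per arm and 79.1% at 17 per arm. So 36 is the smallest total under equal allocation that reaches 80%. The sample size statement is sound, and the present point does not touch it.

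**Step 2. What the contrast computes.** Sorted levels are (0, 1) = (placebo, levosimendan). Hence

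(1)(mean placebo) + (-1)(mean levosimendan) = placebo minus levosimendan.

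**Step 3. Size at the design values.**

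- SE = 5 × √(2/18) = 1.667
- df = 36 - 2 = 34; t(0.975, 34) = 2.032
- Half-width of the 95% CI = 2.032 × 1.667 = 3.387

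| Coefficients | Quantity | Estimate | t | p | 95% CI |
|---|---|---|---|---|---|
| 1, -1 (as written) | placebo - levosimendan | +4.90 | +2.94 | 0.006 | 1.51 to 8.29 |
| -1, 1 (as the label reads) | levosimendan - placebo | -4.90 | -2.94 | 0.006 | -8.29 to -1.51 |

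A data set built to have exactly these means and SDs, fitted with the over-parameterised GLM and both contrast vectors, gave the same results.

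**Step 4. Which output is affected.** The `MODEL` statement has no `CLPARM`, so the labelled `ESTIMATE` line prints no interval; the interval in the first row is shown only for comparison. The one interval for the difference that the code does produce comes from `LSMEANS` with `PDIFF CL`. That interval also runs placebo minus levosimendan, but it is indexed by level and does not carry the misleading label.

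**Step 5. Dependence on a format.** If the variable carried a text format, the default ordering would place Levosimendan before Placebo. Then 1, -1 would match the label and -1, 1 would be wrong. The sign therefore depends on something the code leaves unfixed.

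**Step 6. Reach, if the line is reused.** From section 2.3.2: cardiac index 2, PVR 2, mean pulmonary artery pressure 2, right atrial pressure 2 (each at rest and with exercise), and PCWP supine and with legs elevated, counted as 1 or 2. That makes 9 or 10 hemodynamic comparisons, plus walking distance.

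**The case against.** The strongest reply is that nothing inferential changes: p-value, standard error, power and arm means are identical, and the primary decision at the two-sided 5% level is the same. That is correct, and it limits the severity.

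Next, the code is an example, the prose model in section 3.4.1 is right, and detailed specifications sit elsewhere. This stands in part: the defect bites only if the line is used as written. But it is the only code the SAP gives, it is for the primary endpoint, and sample code exists to be followed.

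A format stored on the data set would not appear in the step, so the level order is inferred. That is also true, though the SAP shows only 0/1 coding. The possibility argues for fixing the order explicitly, because merely swapping the coefficients could bring in the very error it is meant to remove.

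The label says versus, not minus, and section 2.2.3 states the effect as a positive number. That number can be read as a magnitude. With no direction stated anywhere, it does not justify printing a reduction as a positive value under a label that names levosimendan first.

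The same output prints the arm means and, through the `E` option, the coefficients, so a careful reader could catch the slip. That helps only someone who checks. Finally, section 3.4.2 reuses the model and does not mention the `ESTIMATE` statement, so the spread to the secondary endpoints is conditional and is presented here only as such.

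**Conclusion.** The point holds. As written, the code contradicts itself: given its stated coding, the labelled primary contrast has the opposite sign to its label, and no sentence in the SAP settles the direction. At the design values the printed estimate is +4.9 mmHg where levosimendan minus placebo is -4.9 mmHg. Only the sign of the estimate and of its t value differs.

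This rests on two assumptions: the treatment variable is unformatted numeric 0/1, as the code comment shows, and the line is run or copied unchanged. It is not a threat to the validity of the test or to the sample size. It should be fixed because it concerns the sign of the primary estimate as carried into tables.

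**What to change.** In the section 3.4.1 code:

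1. Keep the treatment variable as unformatted 0/1 and write `PROC GLM ORDER=INTERNAL`, so that a format added later cannot reorder the levels. Do this before touching the coefficients.
2. Change the contrast to `ESTIMATE 'LEVOSIMENDAN - PLACEBO' TREATMENT -1 1 / E`.
3. Add `CLPARM` to the `MODEL` statement, so that the labelled estimate carries its 95% CI.
4. In `LSMEANS`, use `PDIFF=CONTROL('0')`, so that its difference is also taken against placebo. If a format is attached, give the formatted placebo value instead.

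Add one sentence to the text of 3.4.1: the treatment difference is levosimendan minus placebo, and for PCWP negative values favour levosimendan. If the code is reused for the secondary endpoints, keep the same direction of subtraction.

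The cost is four code statements and one sentence. Data collection, the test, the sample size and the power are unaffected.
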